6.2 Safety Population

The safety population will consist of all participants who received study treatment. Analyses will be based on actual treatment received.

6.3 Supplementary ePatch Analysis Sets

To conduct supplementary analyses of the primary efficacy and specified secondary efficacy variables, two Supplementary ePatch Analysis (SEA) Sets will be defined. Literature suggests that a majority of POAF occurs within one week post-operation (Aranki *et. al.*, 1996). The first SEA set will analyze participants without substantial missingness for their ePatch data during the first week post-surgery. The second SEA set will analyze participants that additionally are without substantial missingness for their ePatch data during the first 30 days post-surgery. A threshold of 80% of the expected analyzable time will be used to define "without substantial missingness". The two SEA sets are defined as follows:

- SEA-7 consists of all randomized participants who received study treatment and have at least 134.4 hours (5.6 days) of analyzable time of ePatch data for patch "2.1" (the patch expected to be worn for the first 7 days post-surgery).
- SEA-30 consists of all randomized participants who received study treatment and have at least 134.4 hours (5.6 days) of analyzable time of ePatch data for patch "2.1" and have at least 576 hours (24 days) of analyzable time during the first 30 days post-surgery.

Analyses will be based on randomized treatment.

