## 4. Study Design

## 4.1. Overall Design

This is a multi-center, randomized, double-blind, placebo-controlled, parallel group, dose-ranging study to evaluate the efficacy and safety of botulinum toxin type A (AGN-151607) injections into the epicardial fat pads, foci of ganglionic plexi, to prevent POAF in participants undergoing open-chest cardiac surgery. It is projected that a total of approximately 20 to 40 sites (North America and Europe) will enroll a total of approximately 330 participants for this Phase 2 study.

There will be a total of 3 intervention arms randomized in 1:1:1 fashion to receive a one-time injection of:

- 125 U of AGN-151607 (25 U per fat pad)
- 250 U of AGN-151607 (50 U per fat pad)
- Placebo

The randomization will be stratified by age ( $< 65, \ge 65$  years) and type of surgery (presence/absence of valve surgery).

This study intervention will be the administration of a one-time injection of either placebo or AGN-151607 during the open-chest surgery. Primary and secondary efficacy assessments will be performed through Day 30. Additional and exploratory assessments will be assessed through Day 367. All participants will be followed through Day 367 for safety assessments. POAF usually occurs within 2 to 5 days of surgery. However, Pokushalov et al (Pokushalov 2015), found in their study that episodes of POAF were recorded up to 18 days after surgery. Therefore, a 30-day cut off for the primary endpoint is appropriate to mostly fully capture occurrences of POAF. Assessments of clinical benefits and resource-utilization are customarily over a period of 60 days post-surgery (Gillinov 2016). Accordingly, a 60-day cut off was selected for this study to capture resource-utilization outcomes. Finally, based on prior clinical data, the effect of botulinum toxin type A is estimated to be 3 to 6 months. There will be a 12-month follow-up for the study.

Inflammation plays a key role in the etiology of multiple cardiac conditions including the development of POAF. The mechanism of action of AGN-151607

Approximately 400 participants will be screened to achieve approximately 330 randomly assigned to study intervention, in order to have an estimated 300 participants complete all the efficacy assessments up to Day 60 (100 participants per intervention group; Section 9.2).

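### SEA-7 and SEA-30 test first-week completeness by hours on patch 2.1, not hours in the first week, so a late-started patch passes with well under 80% of the week recorded

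*SAP*

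**What the plan says.** SAP 6.3 gives the purpose of the first supplementary set: "The first SEA set will analyze participants without substantial missingness for their ePatch data during the first week post-surgery". It then fixes the standard: "A threshold of 80% of the expected analyzable time will be used to define" adequate completeness.

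The membership rules follow. For SEA-7, randomized and treated participants must "have at least 134.4 hours (5.6 days) of analyzable time of ePatch data for patch" 2.1. A parenthesis describes that patch as "the patch expected to be worn for the first 7 days post-surgery". SEA-30 repeats the patch condition and adds that participants must "have at least 576 hours (24 days) of analyzable time during the first 30 days post-surgery".

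Other parts of the plan bear on how these rules work:

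- SAP 10.0 keeps all interpretable patch data even when the patch was worn off schedule, does not impute missing patch data, and counts post-surgery time from ICU admission for the index surgery.
- SAP 6.1 admits a participant to the mITT population on a single post-dose ePatch ECG by Day 30.
- SAP 10.1 and 10.2 use SEA-7 and SEA-30 for the primary endpoint, time to first AF and each AF-duration endpoint. SAP 10.3 uses SEA-30 for AF counts.
- On timing, Protocol 4.1 says "POAF usually occurs within 2 to 5 days of surgery", and SAP 6.3 says "Literature suggests that a majority of POAF occurs within one week post-operation".

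**The concern.** The purpose is stated in calendar time and the rule in hours on one labelled patch. The only link between the two is the parenthesis, and that records an expectation rather than a condition. A set meant to deal with missing monitoring has to work precisely when wear did not go as expected. In the same paragraph, SEA-30's second condition does use a window counted from surgery.

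What is at stake is the check on missing patch data. With an mITT entry condition of one ECG and no imputation, AF that occurs while no patch is recording is in effect counted as no AF in the binary primary endpoint. SEA-7 and SEA-30 are the planned way to see whether the result survives among adequately monitored participants. If the sets can hold participants who were poorly monitored in week 1, they do not answer that question cleanly.

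**Working it through.** **Inputs.** Week 1 is 7 × 24 = 168 h and the primary window is 30 × 24 = 720 h. The completeness threshold is 80% (SAP 6.3). Time zero is ICU admission (SAP 10.0).

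**The plan's own figures.** 0.80 × 168 = 134.4 h and 0.80 × 720 = 576 h. Both reproduce exactly, so the thresholds are those of a first-week and a 30-day window. Only the quantity compared with 134.4 h is different.

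**Late start.** Assume patch 2.1 starts L hours after time zero and gives 168 analyzable hours, with later patches gap-free to 720 h.

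- Hours on patch 2.1 = 168 for every L, so the written SEA-7 condition is always met.
- Week-1 coverage = (168 − L)/168 for L up to 168. It is at least 80% only if L ≤ 168 − 134.4 = 33.6 h.
- Thirty-day hours = 720 − L. This is at least 576 only if L ≤ 144 h.

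| Start L (h) | Week-1 hours | Coverage | SEA-7 as written | SEA-30 as written | True 80% week-1 rule |
|---|---|---|---|---|---|
| 0 | 168 | 100% | in | in | met |
| 24 | 144 | 85.7% | in | in | met |
| 33.6 | 134.4 | 80.0% | in | in | met |
| 48 | 120 | 71.4% | in | in | not met |
| 72 | 96 | 57.1% | in | in | not met |
| 120 | 48 | 28.6% | in | in | not met |
| 144 | 24 | 14.3% | in | in (exactly 576 h) | not met |
| 168 | 0 | 0% | in | out (552 h) | not met |

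**Overlap with the usual onset period.** Reading 2 to 5 days as elapsed hours 48 to 120 (72 h), a start at 48 h misses none of it, a start at 72 h misses 24/72 = 33%, and a start at 120 h misses all of it. Counting the day of surgery as Day 1 moves the period to hours 24 to 120 (96 h). The same starts then miss 24/96 = 25%, 48/96 = 50% and all of it.

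**Early replacement.** Assume patch 2.1 starts at time zero and is replaced without a gap at S hours by a patch with a different label. Hours on 2.1 = S, so the written condition fails whenever S < 134.4. At S = 96 h the participant has 168/168 h of week 1 and 720/720 h of the 30 days, yet is outside both sets. If the replacement also counts as 2.1, this problem disappears.

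**The case against.** **Wear as scheduled.** The schedule of activities starts the ECG patch on Day 1. If patch 2.1 goes on at time zero and is worn for the week, the two rules agree. No passage reports late or replaced patches. This stands: the table shows what the rule allows, not what happened.

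**The label.** The documents do not define the numbering. If 2.1 names a scheduled wear slot rather than one device, a replacement's hours would count and nobody fully monitored would be excluded. A reader might infer that such participants are certainly lost; the text supports that only conditionally. The late-start problem does not depend on the label.

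**The AF peak.** A reader might infer that the sets generally admit people unmonitored when AF is most likely. The arithmetic does not support that. Delays of 48 or 72 h leave much or all of days 2 to 5 recorded; only a start at about 120 h or later misses the whole period. A 24-hour delay loses 14% of the week, which is inside the 20% allowance and shows no defect.

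**Informative replacement.** It is also tempting to suppose that early patch changes go with AF or its treatment. Nothing in the documents says so, and the point does not need it.

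**Other safeguards.** SAP 10.2 adds a Cox model adjusted for analyzable time and censors at the last recorded data. SAP 10.0 reports analyzable time by arm. SAP 10.3 uses analyzable time as an offset for AF counts. These help for their own endpoints, but none restricts the binary primary analysis to well-monitored participants. The beta-blocker-withdrawal set does not either, since it needs only one ECG.

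**Device clocks.** SAP 15.8 reports clock resets, and patch-hour totals avoid calendar times. But it also gives a correction. SEA-30's 576-hour condition and the primary endpoint's own 30-day window already rely on those times. Differences of 30 days or less stay unadjusted, which is a limitation the existing windows share.

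**Conclusion.** The point holds as a mismatch between the stated purpose of the sets and their definition. For SEA-7, any 7-day patch 2.1 starting after 33.6 h qualifies with less than 80% of week 1 recorded, with no upper limit on the delay. For SEA-30 the delay is limited to 144 h, where 14% of week 1 is covered. These figures assume a full 168 analyzable hours on patch 2.1 and gap-free wear afterwards. The wrongful-exclusion half holds only if a replacement patch is not labelled 2.1.

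The consequence is limited. The affected analyses are supplementary, the number of participants concerned is unknown, and no shift in any estimate can be derived from the documents. A reader might conclude that the primary result is biased by this; it is not, because that analysis uses the mITT population, whose definition does not involve patch 2.1. The definition should still be corrected, because no other planned analysis restricts the binary primary endpoint by monitoring completeness.

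**What to change.** Redefine the sets in SAP 6.3, keeping both thresholds:

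- SEA-7: randomized and treated participants with at least 134.4 analyzable hours, from any patch, within 0-168 h after the post-surgery reference time.
- SEA-30: SEA-7 members who also have at least 576 analyzable hours, from any patch, within 0-720 h.

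Take the reference time as the ICU admission date and time, using the SAP 10.3 imputation (end of study drug administration) when it is missing. State that the same substitute applies to participants never admitted to the ICU, as SAP 10.3 already does for their hospital stay. Use patch times after the SAP 15.8 adjustment. Under this rule the latest qualifying start for week 1 is 33.6 h, and gap-free participants with an early patch change are included whatever the label means.

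The cost is two sentences and one extra derivation from data already collected. The small downside is reliance on corrected device clock times.

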6.4 Beta Blocking Agent Withdrawn ePatch Analysis Set

To conduct supplementary analyses of the primary efficacy and specified secondary efficacy variables within the subgroup of patients that had a beta blocking agent withdrawn post-surgery, the Beta Blocking Agent Withdrawn ePatch Analysis Set will be defined. The Beta Blocking Agent Withdrawn ePatch Analysis Set consists of all randomized participants who received study treatment, have at least 1 post-dose ECG (by ePatch) by Day 30 post-surgery, and had a beta blocking agent at baseline or after surgery that was withdrawn within 3 days post-surgery and no replacement (no new beta blocker prescription) within 7 days post-surgery. Analyses will be based on randomized treatment.

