## 4.2. Scientific Rationale for Study Design

This is a randomized, double-blind, placebo-controlled, dose-ranging study to assess the efficacy and safety of a one-time injection of AGN-151607 in open-chest cardiac surgery participants. The use of placebo is justified as all participants will receive standard-of-care therapies, such as beta-blockers. Participants who experience POAF during the trial will be treated as per investigator judgement and local standards of care. All medications and procedures will be recorded. AF symptoms and quality of life outcomes will be collected through patient reported assessments.

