#### 6.5.3. Rescue Medicine or Procedure

There will be no rescue medication provided by the sponsor for the study.

Standard-of-care will be used at investigator discretion. The study site will supply medications that will be obtained locally, eg, antiarrhythmics drugs, anticoagulants (eg, anti-vitamin K agents, heparin) and rate-control medication (eg, esmolol, metoprolol, diltiazem).

Standard-of-care is allowable at any time during the study. The date and time of any medication administration, as well as the name, indication, and dosage regimen of the medication (ie, dose, route of administration, and frequency), should be recorded.

An intervention to treat an arrhythmia is allowed during follow-up as clinically warranted in the judgement of the treating physician and/or site-based investigator physician.

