10.1 Primary Efficacy Variable

For primary efficacy consideration, POAF will be defined as any continuous episode of AF lasting 30 seconds or more during the first 30 days post-surgery. The primary efficacy variable is the percentage of participants with at least 1 continuous AF episode \geq 30 seconds during the first 30 days post-surgery.

For each of the AGN-151607 doses of 125 U and 250 U, the null hypothesis is that there is no difference between that dose group and placebo in the percentage of participants with at least 1 continuous AF episode \geq 30 seconds during the first 30 days post-surgery. The alternative hypothesis is that there is a difference between the AGN-151607 dose group under consideration and placebo.

The proportion of participants with at least 1 continuous AF episode \geq 30 seconds during the first 30 days post-surgery will be presented for each treatment group. Between-group comparisons will be performed using the Cochran-Mantel-Haenszel (CMH) test for general association stratified by type of surgery (presence or absence of valve surgery) and age group (< 65 or \geq 65 years). P-values, adjusted Mantel-Haenszel (MH) odds ratios and relative risks (and their corresponding 95% confidence intervals) will be presented for each comparison of AGN-151607 versus placebo. Exact (Clopper-Pearson) 95% confidence intervals of the observed proportion will be presented for each treatment group. In addition, exact unconditional 95% confidence interval (using the score method) for the difference in observed proportion between each AGN-151607 dose group versus placebo will also be presented.

For the primary efficacy variable, supplementary analyses will be performed based on the Supplementary ePatch Analysis Sets (SEA-7 and SEA-30) and the Beta Blocking Agent Withdrawn ePatch Analysis Set. The supplementary analyses will use the same methods described for the primary analysis.

For the primary efficacy variable, subgroup analyses will be performed using the same methods described for the primary analysis based on the correct stratification group (with the other stratification factor used for the stratified CMH test):

- type of surgery (presence or absence of valve surgery)
- age group (< 65 or \geq 65 years)]

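### The Beta Blocking Agent Withdrawn set is defined by post-injection events through Day 7 that AF itself can trigger, yet it receives the full primary-analysis methods

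*SAP*

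**What the plan says.** SAP 6.4 builds the set from randomised, treated participants with at least one post-dose patch ECG by Day 30 who had a beta blocker, either at baseline or after surgery, that was "withdrawn within 3 days post-surgery and no replacement (no new beta blocker prescription) within 7 days post-surgery". No exception is made for a beta blocker started because of AF.

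SAP 10.1 defines the outcome: "POAF will be defined as any continuous episode of AF lasting 30 seconds or more during the first 30 days post-surgery". It states that "supplementary analyses will be performed based on the Supplementary ePatch Analysis Sets (SEA-7 and SEA-30) and the Beta Blocking Agent Withdrawn ePatch Analysis Set", and "The supplementary analyses will use the same methods described for the primary analysis". Those methods are the stratified CMH p-value, the Mantel-Haenszel odds ratio and relative risk, and an exact interval for the difference in proportions.

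Four further statements bear on the point:
- Protocol 4.1, on timing: "POAF usually occurs within 2 to 5 days of surgery".
- SAP 6.3, on timing: "Literature suggests that a majority of POAF occurs within one week post-operation".
- Protocol 4.2, on management: "Participants who experience POAF during the trial will be treated as per investigator judgement and local standards of care".
- Protocol 6.5.3 includes "rate-control medication (eg, esmolol, metoprolol, diltiazem" among the locally supplied standard-of-care drugs.

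SAP 10.3 also lists the same yes/no withdrawal status among the items to be described by treatment group. The version history (SAP 17.0) shows that the set came in with Amendment 2.

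**The concern.** Membership is settled by what happens after injection: withdrawal by Day 3, then seven days without a new beta blocker. The outcome is counted over those same days. Take a participant whose beta blocker is stopped on Day 1, who goes into AF on Day 3 and is given metoprolol. That participant has a primary-endpoint event and leaves the set because of it. A comparable participant who stays in sinus rhythm is kept.

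An analysis set should not be shaped by the outcome analysed in it. If it is, the proportions no longer describe the intended patients and the groups compared are no longer those that randomisation created. The SAP sets no landmark, makes no adjustment and adds no caveat. The output would therefore look like any other subgroup result, with a formal p-value and effect estimates.

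**Working it through.** **1. The plan's own figure.** SAP 13.0 states about 80% power with 100 per group, 47.8% vs 27.8%, two-sided 0.05. The mean rate is 0.378. The null standard error is √(2 × 0.378 × 0.622 / 100) = 0.0686. The alternative standard error is √((0.478 × 0.522 + 0.278 × 0.722) / 100) = 0.0671. With continuity correction, power = Φ[(0.200 − 0.010 − 1.96 × 0.0686) / 0.0671] = 79.6%; without it, 83.6%. The stated figure reproduces. The documents give no size, event rate or power for the beta-blocker set, so the planning rates serve below as illustrative true rates.

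**2. Windows side by side.**

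| Element | Days after surgery |
|---|---|
| Withdrawal of beta blocker | to 3 |
| No new beta blocker | to 7 |
| Usual timing of POAF (protocol 4.1) | 2 to 5 |
| AF counted as outcome | to 30 |

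**3. Selection model**, among participants already withdrawn by Day 3. Let p be the true AF risk, f the share of AF cases given a new beta blocker by Day 7, and r the same share among those without AF.

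AF rate in the set = p(1 − f) / [p(1 − f) + (1 − p)(1 − r)]

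The documents give neither f nor r; both are assumed.

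**4. Same selection in both arms, f = 0.50, r = 0.**
- Placebo: 0.478 × 0.5 = 0.239; 0.239 / (0.239 + 0.522) = 31.4%.
- Active: 0.278 × 0.5 = 0.139; 0.139 / (0.139 + 0.722) = 16.1%.
- Retained: 0.239 + 0.522 = 76.1% of placebo and 0.139 + 0.722 = 86.1% of active.

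| Measure | True | In the set |
|---|---|---|
| Risk difference (points) | −20.0 | −15.3 |
| Relative risk | 0.58 | 0.51 |
| Odds ratio | 0.42 | 0.42 |

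The risk difference shrinks while the relative risk moves away from 1.

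**5. Range.** Write f = s × q (with r = 0), where s is the share of AF arising by Day 7 and q the chance that such AF leads to a new beta blocker by Day 7. SAP 6.3 says only that s is a majority. Assume s from 0.6 to 0.9 and q from 0.10 to 0.75, so f runs from 0.06 to 0.675. The risk difference then runs from −19.7 to −11.8 points and the relative risk from 0.57 to 0.49; the odds ratio is 0.42 throughout. At s = 0.8 and q = 0.5 the rates are 35.5% vs 18.8%, a difference of 16.7 points.

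**6. Beta blockers restarted for other reasons.** With s = 0.8, q = 0.5 and r = 0.30, f = 0.8 × 0.5 + 0.2 × 0.30 = 0.46. The rates are 41.4% vs 22.9%, a difference of 18.5 points. If prescribing is unrelated to AF (f = r), there is no distortion.

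**7. When the odds ratio moves.** From the formula in step 3:

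OR in the set = true OR × [(1 − f active) / (1 − f placebo)] × [(1 − r placebo) / (1 − r active)]

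Equal selection cancels. With r = 0, a true rate of 47.8% in both arms and no drug effect:

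| Assumption, placebo vs active | Rates in the set | OR |
|---|---|---|
| q = 0.5 vs 0.5, s = 0.8 | 35.5% vs 35.5% | 1.00 |
| q = 0.5 vs 0.3, s = 0.8 | 35.5% vs 41.0% | 0.76 / 0.60 = 1.27 |
| q = 0.3 vs 0.5, s = 0.8 | 41.0% vs 35.5% | 0.60 / 0.76 = 0.79 |
| s = 0.8 vs 0.5, q = 0.5 | 35.5% vs 40.7% | 0.75 / 0.60 = 1.25 |

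With a true odds ratio of 0.42, the second and third rows give 0.53 and 0.33.

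**The case against.** The other side has substantial points.

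- **Odds ratio and test.** If AF leads to a beta blocker equally often in each arm, the odds ratio is preserved and the null test stays valid. Investigators are blinded (protocol 6.3), so without a drug effect nothing in the documents produces a systematic gap in prescribing. This stands. It does not protect the risk difference or relative risk under a real effect, and a drug that changes AF timing or severity could alter prescribing even under blinding.
- **Size.** Treatment is discretionary, the endpoint counts episodes as short as 30 seconds, and diltiazem would not trigger exclusion. Beta blockers are also general standard of care, so r is unlikely to be zero. All of this pulls towards less distortion, as step 6 shows.
- **Direction.** SAP 6.4 also admits a beta blocker begun after surgery and withdrawn within three days. A short course for early AF could therefore bring a participant into the set. The model covers removal only, so a general rule that the arm with more AF loses more events does not follow.
- **Visibility.** The SAP 10.3 tabulation would reveal unequal membership. It would not correct the estimates.

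A reader might also infer that the SAP presents this subgroup as the clinically most relevant one. It does not: the set is one of several supplementary sets and is given no ranking. A reader might infer that toxin-related bradycardia drives withdrawal, because bradycardia is on the list of possible distant-spread terms in SAP 11.1. Nothing in either document links that term to stopping a beta blocker.

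**Conclusion.** The flaw in the definition is plain from the text: membership depends on events through Day 7 that AF can trigger, and AF in those days is part of the outcome. If AF prompts prescribing, and removal of treated AF cases is the dominant path, AF proportions in the set are too low. Under the planned effect, the risk difference and relative risk are then distorted: 15.3 instead of 20.0 points in the illustration, and 11.8 to 19.7 points over the assumed ranges.

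It is tempting to go further and say that the set will hide a real effect or create a false one. The documents do not support that. Bias in the odds ratio or p-value needs an arm difference in prescribing or AF timing, which is plausible for an active drug but not shown, and it could run either way. Size and direction cannot be fixed without f, r and the number in the set.

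The primary mITT analysis does not use this rule, so its conclusion and its alpha are untouched. The point concerns one supplementary analysis and is worth correcting because the correction is cheap.

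**What to change.** Preferred: replace the set in SAP 6.4 with a subgroup defined by beta-blocker use before surgery. That status is fixed before injection and comes from prior-medication data already collected (SAP 8.0). The SAP 10.1 methods can then be applied unchanged.

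If post-operative withdrawal is the question of interest:
- define status at the end of Day 3;
- delete the seven-day no-replacement clause;
- count only first AF after Day 3, among participants free of AF at that landmark;
- label the result a non-randomised, post-randomisation subgroup.

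The cost is a short SAP edit and one derivation; patient care and data collection do not change. Each option has a price. The baseline subgroup answers a somewhat different question from withdrawal after surgery. The landmark version loses AF before the landmark, which matters when POAF is expected mainly on Days 2 to 5. It also conditions on being AF-free at Day 3, which treatment may itself affect; hence the label.
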